4.1. Targeted Population Justification

* Describe the population that will be targeted or excluded and provide justification.

This study will target an elderly population (ages 50 to 80 years old). Given the intervention being tested is intended for older adult smokers, it is necessary that we recruit individuals from this age group. This population of smokers are particularly at risk for all of the known health effects of smoking, including dementia. Participants with self-reported history of MCI or dementia will be excluded to ensure ability to provide consent.

Special Populations Justification

1. Justification

If more than one special population is enrolled, separate justifications should be provided for each unique population.

- * What is the justification for the inclusion of these subjects?

Older adults/elderly are the main focus of this study and therefore required to be included.

2. Safeguards

Include the measures that will be taken to minimize any potential coercion or undue influence in recruitment and ongoing participation in the study.

- * Describe the additional safeguards that have been included in this study to protect the rights and welfare of these subjects.

We will only include participants with the cognitive capacity to consent as defined by lack of MCI or dementia diagnosis.

Recruitment Methods

1. Recruitment Plan

This description should address what methods will be used, when and how often they will be used, and how many times potential subjects will be contacted.

* Describe the recruitment plan for this study.

Participants will be recruited nationally (within the United States) primarily via social media advertisements. Should these efforts fail, we will use flyers, web banners, and television advertisements. If television advertisements are used, we will upload a TV ad script with a COP at that time. The English translation of the La Comunidad web banner ad is as follows: "Are you 50 to 80 years old and smoke? Get paid up to \$75 for sharing your opinions on smoking in English for a University of Wisconsin research study via phone. You do NOT need to quit smoking. Click here!" Those interested in participating in the study will complete the online qualtrics screener or call the provided contact information to enroll in the study directly with UW-CTRI staff. Upon contacting UW-CTRI we will confirm their location via their provided address.

2. Recruitment Material Upload

Upload recruitment materials such as recruitment emails, letters, phone scripts, brochures, or advertisements.

-  facebook ad_v3(0.04)
-  LaComunidad-Ad_v1(0.01)
-  MCAS_TVadscript_v1_09_13_2023(0.01)
-  recruitment flyer_v3(0.04)

3. Approved Recruitment Database Usage

* Are you using an IRB approved recruitment database to disseminate recruitment materials or to contact subjects?

Yes No

Subject Screening

1. Preliminary Eligibility Screen

* Will subjects undergo a preliminary screen to determine basic eligibility?

Yes No

1.1. Screening Materials

* Upload a copy of the screening questionnaire.

 Phone Screen v4(0.05)

 qualtrics screen_v4(0.04)

1.2. Data Retention

If you are retaining screen data, the previously uploaded questionnaire/script should address this and include authorization language for maintaining PHI if HIPAA applies.

* Will you be retaining screen data from subjects who do not enroll in the study?

Yes No

1.2.1. Retention Justification

Describe the purpose of retaining the screen data.

Phone screen data will be maintained separately from the participant database once these data are not needed for study operations.

1.2.2. Data Storage and Maintenance

Describe where the screen data will be maintained. If these data will be retained in a recruitment database, indicate whether the development of a recruitment

database is the purpose of this study OR provide the IRB protocol number of the database.

All phone screen data for those who do not consent to participate in the study will be maintained in HIPAA-de-identified form until the end of the study and then destroyed.

2. Planned Study Procedures Before Obtaining Consent

Examples include fasting, discontinuing medications, etc.

* Will there be any procedures performed before informed consent is obtained from subjects (apart from screening)?

Yes No

Remuneration and Costs

1. Payment

* Will subjects be compensated to participate in the study?

Yes No

1.1. Travel and Other Expenses

* Is payment limited to covering travel expenses and other costs incurred by subjects as a result of study participation?

Yes No

1.2. Payment Plan

Include the amount of payment(s), proration, multiple payment schedules, etc. Payments to research participants must adhere to campus policy. Questions about payment methods can be directed to Business Services.

* Describe the payment plan.

Participants will be paid \$35 for their time and effort for the first phone interview and \$40 for the second interview (max. possible/person=\$75). Additionally, up to 20 participants will be invited to participate in a brief qualitative interview following the second survey interview. Those who participate in this optional additional interview will be paid \$25 more for their additional time and effort.

1.3. Child/Parent Payment

* Are any payments being offered to child subjects?

Yes No

1.4. Nonmonetary Compensation

* Will nonmonetary compensation be offered?

Yes No

2. Costs

* Will subjects incur any costs as a result of study participation (pharmacy preparation fees, payment for a device, billing of study procedures to subjects insurance)?

Yes **No**

Privacy and Confidentiality

1. Privacy Plan

Privacy is defined in terms of having control over the extent, timing, and circumstances of sharing oneself (physically, behaviorally, or intellectually) with others. In the context of research, this primarily pertains to methods used to obtain information about subjects or the setting in which research takes place.

- * Explain how the subjects' privacy will be protected. (e.g., research intervention is conducted in a private room).

All communications regarding research activities will be directly with the consented participant and from a location where privacy can be maintained. Participant study data will be collected by research personnel and will be stored on secure, password protected servers. Data will be accessible only to assigned study staff for their study function; computer workstations will be password-protected, and thus secured from unauthorized use. A Certificate of Confidentiality will be issued for the study.

2. Level of Identifiability

- * Select how subjects are identified in the data. Check all that apply.

Directly: Direct Identifiers stored on data (e.g., name, initials, phone number, SSN, or medical record number, stored on data)

2.1. Necessity of Data

- * Explain the necessity of collecting or maintaining data linked to subjects' identities.

This will allow for study payments to be sent to participants and to contact participants for follow up assessments. Data will be stored in a password protected file on a secure departmental server.

2.2. Retaining Data

- * How long will data linked to subjects' identities be retained?

Subject identify will be linked to data until data collection is complete.

3. Data Protection Plan

Records and data include informed consent documents, case report forms or study flow sheets, survey instruments, database or spreadsheet, screening logs or telephone eligibility sheets, web based information gathering tool, audio/video/photo recordings of subjects, labeled specimens, data about subjects, subject identifiers, etc.

The study team should describe how data confidentiality will be protected. Some measures that are often used and acceptable to the IRB are: using codes so that no direct subject identifiers are recorded on data collection sheets; creating codes for data that are not based on subject identifiers (i.e., avoiding codes that include subject initials or are based on birth dates); and destroying the link to the code as soon as possible.

* How will the study team protect research records, data, and/or specimens against inappropriate use or disclosure, or malicious or accidental loss, or destruction? Include how and where the data and/or specimens will be stored.

Video and/or audio files will be recorded using a secure device and will be stored in a restricted access folder on the department server. Audio files are for transcription purposes only and will be permanently destroyed as soon as transcription is complete. If names or identifiable information are revealed during the recordings, this information will not be recorded in the transcription. Electronic files will be stored on a secure department server.

Servers at the UW-CTRI Madison office are physically secured in a locked room. Data backups are created nightly and stored in a locked safe. Significant safeguards have been implemented to protect data including virus and adware protection, firewall, access controls and encryption when appropriate such as wireless and remote access. All UW-CTRI staff members have completed HIPAA and human subjects training and are aware of the sensitivity of study-related data. The UW-SMPH has developed school-wide data security policies and procedures. UW-CTRI data security policies and procedures conform to those of the UW-SMPH. No publications or presentations resulting from this research program will contain any identifying information about individual participants. Following cleaning and verification of data at the conclusion of the study, all research data will be placed in a de-identified data set at UW-CTRI.

4. Certificate of Confidentiality

If NIH, CDC, FDA, or other federal funding from an agency that automatically issues a Certificate of Confidentiality as part of the terms of the award, answer "Yes".

* Is there a Certificate of Confidentiality (CoC), or will one be obtained, for this research?

Yes No

4.1. CoC Details

* Select the answer that applies to your CoC.

I will rely on a CoC that is included as part of current NIH, CDC, FDA, or other federal funding from an agency that automatically issues a Certificate of Confidentiality as part of the terms of the award.

I will apply for a CoC (there is no NIH, CDC, FDA, or other federal funding from an agency that automatically issues a Certificate of Confidentiality as part of the terms of the award).

I have obtained a CoC.

Retention of Data and or Specimens

1. Future Research Plans

* Will data and/or specimens collected for this study be banked for future research outside the scope of the current project?

Yes **No**

Consent: General

1. Obtaining Consent/Assent

* Will you obtain consent or assent from some or all participants?

Yes No

1.1. Signed Consent/Assent

* Will you obtain signed consent or assent from all participants?

Yes **No**

1.2. Altering Required Elements

* Are you proposing to alter required elements of consent or assent (e.g. required information will not be disclosed, or the research involves deception)?

Yes **No**

1.3. No Consent/Assent

* Are there some participants from whom you will not obtain consent or assent?

Yes **No**

Waiver of Signed Consent

1. Waiver of Signed Consent Process

* Are you requesting a waiver of signed consent for all components of the study?

Yes No

2. Criteria

* Under which of the following criteria does this research qualify for waiver of signed consent? The research presents no more than minimal risk of harm to subjects and involves no procedures for which written consent is normally required outside of the research context.

3. Criteria Justification

* Provide a justification for the criterion selected above.

The research is a benign behavioral intervention that will be of minimal risk to the participants. Data security measures minimize the risk of breach of confidentiality, and the study activities do not normally require written consent outside the research context.

Consent Overview

1. Consent Process

* Describe the consent process, including when and where it will occur and how the consent process will be conducted (e.g., face to face, phone or video discussion) and how consent information will be provided to participants (e.g., in person, mailed/mailed).

Consenting will be done over the phone. After completing the Phone Screen, study staff will use the Study Information Sheet (see uploaded Study Information Sheet) to discuss study procedures and all elements of informed consent including:

- Study sponsor
- Invitation/Summary
- Study purpose
- Study participation, including assessments, schedule of study contacts, and treatment overview
- Risks, Benefits, and Costs
- Payment for participation
- How to revoke authorization
- Confidentiality
- How to contact study staff

We will provide a text copy of the the information sheet to the participants by mail after the initial call. Due to the screening and initial survey assessment occurring in the same call it is not feasible to provide the information to the participants prior to the first call. We will offer to email participants the information sheet if they explicitly ask for it, otherwise it will be mailed to participants.

2. Special Populations Involved

* Will the study enroll participants with limited English proficiency, who are illiterate/low-literacy, or have visual/hearing impairments?

Yes No

3. Qualification Affirmation

* Do you confirm that all study personnel responsible for obtaining informed consent have the following qualifications: 1) are familiar with the details of the study; 2) will ensure subjects are provided with sufficient information to make an informed and voluntary decision about study participation; 3) are familiar with UW-Madison policies regarding

informed consent?

Yes No

Consent and Authorization Upload

1. Consent/Accent Documentation

- E.g., information sheet, consent form, assent form, translated consent documents.
- Please use IRBs informed consent templates to develop consent processes and documents for non-exempt studies.
- For educational and social-behavioral studies, you can use the Consent Form Wizard. The Wizard does not include HIPAA authorization language.

* Upload all consent authorization, and/or assent documents.

 consent process_v2(0.02)

 Study information sheet_v4(0.06)

HIPAA

1. Identifiable Information

* Will the research involve identifiable health information for any reason?

Yes No

1.1. UW Madison Health Care Component or Madison VA

The HCC of the UW-Madison currently includes SMPH clinical departments; School of Pharmacy (clinical units only); School of Nursing; University Health Services (non-student records only); State Laboratory of Hygiene; and Waisman Center (clinical units only). Ensure the PI or any study team members are covered under HIPAA Privacy Rule regulations as part of their appointment.

* Are you or any member of the study team conducting the study under an appointment that is within the UW-Madison Health Care Component (HCC) and/or Affiliated Covered Entity (ACE) or the Madison VA?

Yes No

1.2. HIPAA Authorization

* Will HIPAA authorization for access to the PHI be obtained for all or some subjects, or for only some uses?

Yes, always: HIPAA authorization will be obtained from all subjects with signed documentation.

Yes, sometimes or without signed documentation: HIPAA authorization will not be obtained from some subjects/uses or may be obtained without a signature.

No: HIPAA authorization will not be obtained from any subjects.

1.3. External PHI Access

* Will you access or obtain fully identifiable health information from a health care provider that is not UW or UW Health or the Madison VA, such as Meriter or ACHC, without first obtaining

patient permission or authorization?

Yes **No**

Authorization and Waivers

When sharing fully identifiable health information outside of UW or UW Health or obtaining it from a covered entity that is not UW or UW Health (e.g. bringing PHI from Meriter to a UW workstation to contact for phone screening or to recruit), you may need a partial waiver of authorization and accounting for disclosures may be required. Please consult with the **HIPAA Privacy Officer** and consult the Accounting for Disclosures Guidance found [here](#).

1. HIPAA Requirement Fulfillment

* Please select which option(s) will be applied to fulfill HIPAA requirements.

Request Partial Waiver or Altered Authorization

2. Applicable HIPAA Identifiers

Select which of following identifiers will be associated with the health information you propose to collect for study purposes. Check all that apply to your study. If none of these identifiers will be collected for your study, select 'None of the Above'.

Names

Geographic subdivisions smaller than a state

All elements of dates (except year) related to an individual including:

*Dates of admission, discharge, or service
*Dates of birth or death

Telephone numbers

Electronic mail addresses

Request for Authorization/Waivers

When sharing fully identifiable health information outside of UW or UW Health or obtaining it from a covered entity that is not UW or UW Health (e.g. bringing PHI from Meriter to a UW workstation to contact for phone screening or to recruit), you may need a partial waiver of authorization and accounting for disclosures may be required. Please consult with the **HIPAA Privacy Officer** and consult the Accounting for Disclosures Guidance found [here](#).

1. Altered Authorization

HIPAA authorization for research must be project-specific. Standard clinical consent and authorization does not cover research use. If you will not obtain authorization in writing or seek to significantly modify the standard HIPAA authorization language, an altered authorization is necessary.

* Are you requesting an altered authorization?
 Yes No

1.1. Altered Authorization - Details

Please describe how authorization will be altered.

Verbal authorization

2. Partial Waiver of Authorization

If you will not obtain authorization from any subjects, a full waiver is required.

* Are you requesting a partial waiver of authorization?
 Yes No

3. Type of PHI Records

* Identify the PHI to be used. Select all that apply.

4. Confirm Policy for Sharing PHI Externally

For help, see HIPAA – Privacy & Security Coordinators. Examples of directly identifiable data is data that includes name, MRN, narrative text fields, or a rare condition that can be traced back to an individual.

If you disclose directly identifiable PHI outside the HIPAA covered entity under which you are conducting the study, confirm you will contact the UW Madison HIPAA Privacy Officer or the Madison VA Privacy Officer.

Yes No

5. PHI Protection Plan

* Describe your plan to protect PHI from unauthorized use or disclosure.

Paper files will be stored in a secure campus location and destroyed after data has been entered electronically.

Electronic files will be stored on a secure department server.

Only approved personnel will have access to study data.

6. PHI Destruction Plan

* Describe your plan for destroying identifiers at the earliest possible opportunity.

Identifiers will be destroyed at study closure.

7. Waiver/Alteration Justification

* Explain why the study cannot practicably be conducted without the waiver of authorization or altered authorization.

Signed consent will not be obtained in the interest of limiting the number of study documents with the participant's name and participation in the study activities

indicates consent and authorization.

Only the minimum necessary PHI needed will be collected.

8. Limitations Confirmation

* Federal law prohibits the re-use or disclosure of PHI in connection with this research to any person or entity other than those authorized to receive it, except: (1) as required by law; (2) for authorized oversight of the research; or (3) in connection with other research for which the HIPAA Privacy Rule permits the PHI to be used or disclosed. Do you agree to abide by these limitations in order to obtain a waiver of authorization?

Yes No

Audio/Video Recordings and Photographs

1. Recordings Collected

* Select which of the following will be collected for this study. Check all that apply.

Audio recordings

Video recordings

Photographs

2. Identifiable Recordings

E.g., full face photo/video, audio recording of first and last name, or other individually identifiable information.

* Will the subject be identifiable in the audio/video recording or photograph?

Yes **No**

3. Retain Recordings

* Will the audio/video recordings or photographs be retained beyond the conclusion of this study?

Yes **No**

4. External Transcription

* Will anyone outside the study team transcribe audio recordings?

Yes No

4.1. Transcriber Details

* Indicate who will perform the transcription.

Transcription will be done by a professional transcription service.

Interviews, Focus Groups, Surveys, Questionnaires

1. Tool Details

* Describe the interview tools, questionnaires, or surveys that will be used. Click the add button to provide information about each tool to be used.

View	Tool Description	Optional Qualitative Interview
	Tool Standardized	No
	File name	Outline of Qualitative Interviews_V1_2023.10.13.docx
	Tool Manner	Telephone
	Tool Manner Other	No Value Entered
	Date Modified	10/20/2023

View	Tool Description	Follow Up Survey
	Tool Standardized	No
	File name	MCAS Aim 3 3 Month Follow Up Questionnaire_V2_10_20_23_trackedchanges.docx
	Tool Manner	Telephone
	Tool Manner Other	No Value Entered
	Date Modified	10/20/2023

View	Tool Description	Baseline Survey
	Tool Standardized	No
	File name	MCAS Aim 3 Baseline Questionnaire_V5
	Tool Manner	Telephone

Tool Manner Other	No Value Entered
Date Modified	9/13/2023

2. Cognitive or Psychological Assessment

* Are any of the uploaded instruments used to assess cognitive or psychological status or function?

Yes **No**

Interviews, Focus Groups, Surveys, Questionnaires Cont.

1. Focus Group

* Will the study involve conducting focus groups?

Yes **No**

2. In-Home Visit

* Does the study involve in-home visits?

Yes **No**

Supplemental Information

1. Additional Documents

Provide any additional relevant documents (e.g., data sharing agreements, letters of support, MOUs, site permission letters), if applicable.

-  active control flyer 1(0.01)
-  active control flyer 2(0.01)
-  active control flyer 3(0.01)
-  active control videos(0.01)
-  fear flyer(0.01)
-  fear video(0.01)
-  MCAS Mailing 1 Cover Letter Active Control and Treatment Condition (Groups 1, 2, 4)_v2(0.02)
-  MCAS Mailing 1 Cover Letter No Treatment Condition (Group 3)_v2(0.02)
-  MCAS Mailing 2 Cover Letter Active Control and Treatment Condition (Groups 1, 2, 4)_v2(0.02)
-  MCAS Mailing 3 Cover Letter Active Control and Treatment Condition (Groups 1, 2, 4)_v2(0.02)
-  MCAS Mailing for Follow-up Payment v1_11_8_23.docx(0.01)
-  MCAS Video Group 1 Email 1.docx(0.01)
-  MCAS Video Group 1 Email 2.docx(0.01)
-  MCAS Video Group 1 Email 3.docx(0.01)
-  MCAS Video Group 1 Email 3_V2_10_20_23_trackedchanges.docx(0.01)
-  MCAS Video Group 2 Email 1.docx(0.01)
-  MCAS Video Group 2 Email 2.docx(0.01)
-  MCAS Video Group 2 Email 3.docx(0.01)
-  MCAS Video Group 2 Email 3_V2_10_20_23_trackedchanges.docx(0.01)
-  MCAS Video Group 4 Email 1.docx(0.01)

1.1. Describe Documents

Describe what additional documents were added in 1.

We have added a cover letter to be included with the participants' final study payment.

Final Page

1. Assurance

- The information presented in this application is accurate;
- If the application is being submitted on behalf of the Principal Investigator (PI) rather than by the PI, the information presented was done so with the PI's agreement; and
- The specific aims and description of research (including subject population, subject interventions, collaborators, performance sites, and general scope of work) in this IRB application are consistent with those described in the sources of support listed as providing financial and/or material resources to conduct this study.

* Do you certify the above statements?

Yes No

2. Complete and Submit Application Instructions

To complete and submit this application to the IRB office, please follow the steps below:

- Select 'Finish' or 'Exit' on this page to be directed to the application workspace.
- In the application workspace, click the Submit activity to send the application to the IRB office. NOTE: The Submit activity is only available to certain study team members.

Statistical Analysis Plan

[name] will use SPSS to examine differences in changes in motivation (primary), number of 24 hour quit attempts (secondary), and use of evidence-based treatment (secondary) between groups. Specifically, she will examine differences in mean scores from baseline and follow up between the treatment group and three control groups. Given the pilot nature of this study, we will not be statistically powered to conduct regression analyses. Therefore, descriptive analyses will be the primary analytic method.

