Participants will be randomized to one of four messaging interventions; 1) active control (CDC TIPS from former smokers campaign), 2) active control (American Lung Association campaign), 3) treatment condition including message package focused on the link between smoking and dementia, 4) no intervention control. The messaging intervention will be delivered via mail, which will include a QR code link that will allow participants to view associated motivational video. Participants will then complete the first of 2 telephone survey assessments (lasting ~30 minutes). Participants will then receive three mailers over the next couple of months and will schedule their follow-up call approximately 2.5 months later. At one to two weeks, one month, and two months after this call they will be mailed the corresponding message to their group (no intervention group will not be sent a message package). Follow up telephone assessments will occur within approximately 1-2 weeks following intervention exposure marked by date the intervention mailer was sent.

Up to 20 participants randomized to the intervention condition will complete an additional brief qualitative interview following their second telephone survey assessment (lasting ~20 minutes). The qualitative interview will focus on the perceived impact of the message, preferred number of message exposures, preferred modality of message receipt, and suggested improvement to message content. Health Believe Model (HBM) constructs assessed include: perceived severity, perceived benefits (i.e., efficacy of EBSTs; impact of quitting on ADRD risk), perceived barriers (i.e., knowledge of how to access EBSTs in healthcare setting), and self-efficacy (i.e., confidence in ability to quit in the next 30 days).

4.

Incidental or Adventitious Findings

* Will any study procedures produce incidental or adventitious findings (e.g., imaging scans, laboratory blood tests, depression screening questionnaires, etc.)?

Yes **No**

5. Instruments/Technology Involved (Includes AI/ML Algorithms)

This question is intended to identify projects involving the development or use of medical devices. This does not apply to surveys, questionnaires, or statistical analysis software.

* Are there instruments or technology of any kind, including software, tests run on samples, and algorithms, used or developed in the study?

Yes **No**

Subject Identification: Medical Records

1. Medical Record Use

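### The SAP compares unadjusted baseline and follow-up means without saying who is in them, so unequal loss, most plausible against the no-intervention arm, could distort the treatment difference

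*Combined protocol and SAP*

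**What the plan says.** The Statistical Analysis Plan sets out to "examine differences in changes in motivation (primary), number of 24 hour quit attempts (secondary), and use of evidence-based treatment (secondary) between groups". It then makes this specific: "she will examine differences in mean scores from baseline and follow up between the treatment group and three control groups". Because "we will not be statistically powered to conduct regression analyses", the plan concludes that "descriptive analyses will be the primary analytic method". It names no analysis set, no rule for people without a follow-up call and no adjustment for baseline.

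Under Research Design and Procedures, 3. Study Procedures and Interventions, "Participants will be randomized to one of four messaging interventions". All arms have two telephone surveys, the second about 2.5 months after the first. Contact between the calls differs: "no intervention group will not be sent a message package". The list under Supplemental Information, 1. Additional Documents, agrees. For the no-intervention arm it shows one letter, "MCAS Mailing 1 Cover Letter No Treatment Condition (Group 3)_v2(0.02". For the other three arms the letters run through to "MCAS Mailing 3 Cover Letter Active Control and Treatment Condition (Groups 1, 2, 4)_v2(0.02", and video e-mails are listed for those groups only.

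Risks and Benefits, 5. Procedures to Minimize Risks, foresees skipped activities and withdrawal. No available section gives an expected loss or says how loss will be reported. Remuneration and Costs, 1.2. Payment Plan, gives \$40 for the second interview, with no difference by arm.

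**The concern.** A difference between two group means is a clean measure of change only if the same people are in both. The SAP does not secure this. If the baseline mean covers everyone and the follow-up mean covers only those reached, the comparison mixes real change with a change in who is measured. A contrast between arms is then distorted whenever the arms lose different numbers, or different kinds, of people.

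Unequal loss is a reasonable worry for treatment versus no intervention, because one side has several mailings between the calls and the other has little. Bare group means would not reveal the distortion, and the plan has no step that would correct it. A real benefit could be hidden or a false one created. The secondary outcomes are exposed in another way: attempts and treatment use between the calls are simply unknown for anyone not reached.

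**Working it through.** **Inputs from the documents.** Total 220 (Subject Population, 1. Total Subjects); four arms; two calls. The 220 comes without effect size, SD, power or attrition, so it cannot be reproduced. The allocation ratio is not stated. If it is equal, 220 / 4 = 55 per arm, and the standard error of a difference between two means is sqrt(2/55) = 0.19 SD before any loss.

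**Assumptions (the documents give none of these).** d = share lost in an arm; g = baseline gap, completers minus those lost, in SD units; r = correlation between baseline and follow-up scores.

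**1. Baseline mean of everyone, follow-up mean of those reached, nobody changing.** The baseline mean is (1 − d) × completers' mean + d × mean of those lost. The follow-up mean is the completers' mean. The apparent change is therefore d × g. With the same g in both arms, the false difference (treatment minus no intervention) is (dT − dC) × g.

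| Loss, treatment vs no intervention | g = 0.25 | g = 0.5 | g = 1.0 |
|---|---|---|---|
| 10% vs 20% | −0.025 | −0.05 | −0.10 |
| 10% vs 30% | −0.05 | −0.10 | −0.20 |
| 20% vs 20% | 0 | 0 | 0 |
| 30% vs 10% | +0.05 | +0.10 | +0.20 |

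At 10% vs 30%, a true benefit of 0.20 SD would appear as 0.20 − 0.10 = 0.10 (g = 0.5) or 0.20 − 0.20 = 0.00 (g = 1.0). Equal loss is not always safe: 20% in each arm with gaps of +0.5 and −0.5 gives 0.10 + 0.10 = 0.20 SD.

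A simulation (4,000 runs, 55 per arm, lower baseline motivation more likely to be lost, no mean change) had average losses of 9.6% and 30.1% and gaps of 1.05 and 0.96. It gave −0.19 SD, in line with the formula.

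**2. Paired change in those with both calls.** If every score is unchanged, the artefact is exactly zero. If scores vary between calls with no mean change, completers who start above average drift back by (1 − r) times their excess. The false difference is then about (1 − r) × 0.187, with the opposite sign:

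- r = 0.5: 0.5 × 0.187 = +0.09 SD (simulated +0.09)
- r = 0.7: 0.3 × 0.187 = +0.06 SD (simulated +0.05)

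**3. Follow-up score adjusted for baseline, in those with both calls.** In the same simulations the false difference was about 0.00 SD at each r. With equal variances at the two calls, adjustment also gains precision. The variance factor is 1 − r² against 2(1 − r) for unadjusted change: 0.75 against 1.00 at r = 0.5, and 0.51 against 0.60 at r = 0.7.

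**4. Secondary outcomes.** The plan counts attempts; any attempt is used here for simplicity. Suppose 35% truly attempt in both arms and 15% do among those lost, with losses of 25% (no intervention) and 10% (treatment).

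- Completers: (0.35 − 0.25 × 0.15) / 0.75 = 41.7% and (0.35 − 0.10 × 0.15) / 0.90 = 37.2%, a difference of −4.4 points for treatment.
- Those lost counted as none: 0.3125 and 0.335, a difference of +2.25 points.

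The sign turns on a choice that the SAP does not make. The two results do not bracket the truth. Keep the completer results but let 60% of the lost controls and 10% of the lost treated attempt. The true rates are 0.3125 + 0.25 × 0.60 = 46.25% and 0.335 + 0.10 × 0.10 = 34.5%, a difference of −11.75 points.

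**The case against.** The strongest reply is that the SAP's stated target is change, and paired change in people with both calls is as natural a reading as any. That stands: under it the results in step 1 vanish. But the SAP does not say so, its specifying sentence speaks of mean scores, and step 2 shows that unadjusted paired change is not safe either.

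Second, unequal loss and its direction are conjecture. This also stands. Every arm has the same calls and the same stated payment. The low-contact arm carries less burden. The listed materials include a fear flyer and a fear video, apparently for the treatment arm, and the risk section foresees upset, so loss could be higher there.

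Third, unequal contact touches one contrast of three: the two active controls have the same listed mailings as treatment. This is correct, and it limits the scope.

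Fourth, the possible bias is at most about one standard error over most of the illustrated range, in a descriptive pilot. That bears on severity, but a systematic shift is not shown by the spread of the data and readers could not detect it.

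Fifth, the SAP declines regression for lack of power. This does not answer the point. Baseline adjustment is used here to reduce bias and improve precision, whatever the power.

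**Conclusion.** The concern holds in a limited form. The SAP leaves open who enters the baseline means and plans no adjustment, so its primary comparison is exposed to unequal loss under either reading of change. The illustrative size is 0.05 to 0.20 SD for 10% versus 30% loss and gaps of 0.25 to 1.0 SD if everyone is in the baseline mean, or about 0.05 to 0.09 SD with the opposite sign for paired change in the simulated case. These figures rest on assumed loss, gaps and correlations, and the comparison with 0.19 SD rests on an assumed 55 per arm.

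A reader might go further and infer that the planned analysis will show a false difference against treatment. The documents do not support that: they do not state that baseline means cover everyone, they give no loss in any arm, and they do not say who is likely to leave. Nor do they support extending the unequal-contact argument to the active controls. The change is worth making before analysis; the gap does not by itself invalidate the trial.

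**What to change.** In the Statistical Analysis Plan:

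- State that the primary comparison is the between-arm difference in follow-up motivation, adjusted for baseline motivation, by arm as randomised, given as an estimate with a confidence interval beside the descriptive means. One SPSS analysis of covariance covers all three contrasts.
- Report baseline and follow-up means and paired change for those with both calls, and name that set.
- Tabulate loss by arm, with the baseline motivation of those lost and those retained.
- For quit attempts and treatment use, show the completer result and a result counting those lost as none. Label them two sensitivity scenarios, not bounds.
- Confirm that the first survey precedes the first mailing. The consent process and the mailing schedule imply it, but the order of sentences in Study Procedures can be read otherwise, and adjustment needs a score taken before any message.

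The cost is a little more analysis, a few table rows and two versions of each secondary result. Conduct does not change, because baseline motivation is needed for the planned analysis anyway. Adjustment removes the bias shown above when loss depends only on baseline motivation. It does not repair loss that depends on the unseen follow-up value, which is why loss by arm must be shown.
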